Abstract: Polycystic ovarian syndrome (PCOS) is one of the common endocrine diseases that lead to female reproductive dysfunction. Up to 75% of PCOS patients have endocrine and metabolic abnormalities such as obesity, hyperinsulinemia and hyperandrogenemia. As a classic PCOS drug, CPA/EE is mainly used to adjust estrogen and progesterone levels and menstrual cycle. Recent studies have found that this drug may worsen blood lipids and reduce insulin sensitivity. On the other hand, studies have found that reproductive disorders secondary to metabolic disorders can be improved by correcting metabolic disorders. glucagon-like peptide1 receptor agonist (GLP-1 RA) is a new type of glucagon-like peptide1 receptor agonist, which has a significant effect on the improvement of metabolic disorders in obese patients. This topic aims to study. To observe the effects of metformin combined with CPA/EE or GLP-1RA on blood glucose, blood lipids, sex hormone levels and menstrual cycle in overweight PCOS patients.

Sponsor/Contact Person/Phone Number	Xinqiao Hospital Endocrinology Department/ [name] /[name]
Research department/project leader	Endocrinology Department / [name]
Research category	Clinical research, source: self raised
Title of the study	The Effect of GLP-1 Agonists Versus OCs on Reproductive Disorders and Cardiovascular Risks in Overweight PCOS
NTC Number	NCT03151005
Research duration	3 years
Number of research and design cases in this center	60 cases
Study design	All subjects underwent height, weight, waist and hip, hip circumference, blood pressure, hairy score, blood biochemistry (blood routine, liver and kidney function, electrolyte, thyroid function, fasting blood glucose, glycated hemoglobin, insulin release test, inflammatory markers, sex hormones, eight items), gynecologic color Doppler ultrasound and glucose clamp examination before admission. After informed consent was obtained, 1ml of the remaining plasma was collected and frozen in the refrigerator at -80°C. Patients with $BMI \geq 24 \text{ kg/m}^2$ or waist circumference $\geq 85 \text{ cm}$ were randomly assigned to GLP-1RA + metformin or Diane-35 + metformin. After 1 month, all subjects were examined: height, weight, BMI, waist circumference, hip circumference, waist-to-hip ratio, menstrual history, hirsutism score, diet, exercise frequency and intensity, blood pressure and blood biochemistry. After 3 months, the general condition of all subjects and general biochemical tests such as blood lipid, liver and kidney function, fasting blood glucose, glycated hemoglobin, insulin release test, inflammation markers and gynecological color ultrasound were tested again, and 1ml of plasma was collected and frozen in the refrigerator at -80°C.
Trial objective	
 Provide new treatments for overweight or obese patients with PCOS. Improve PCOS and establish regular menstrual cycles by reducing weight and correcting metabolic disorders.
Name and specifications of the required drugs or equipment Grid, manufacturer, and quantity	Metformin enteric coated tablets: Hebei Tiancheng Pharmaceutical Co., Ltd., trade name: Junshida, dosage: 0.5g orally 3/day; Liraglutide injection: Novo Nordisk, Denmark, trade name: Novo Nordisk, dosage: 0.6mg subcutaneous injection once a day, increased to 1.2mg after 1 week, maximum dose is 1.8 mg/d; Acetylenylestradiol cycloproterenone tablets: Bayer AG, Germany, trade name: Diane-35, dosage: 1 tablet taken orally starting from the first day of the menstrual cycle, Take 1 tablet daily for 21 consecutive days, discontinue for 7 days.
Inclusion and exclusion criteria	
Inclusion criteria : a) clinical diagnosis of PCOS according to the Rotterdam criteria based on the presence of two of three criteria (3) , oligomenorrhea, clinical or biochemical hyperandrogenism, and polycystic ovaries on ultrasound after exclusion of other endocrine causes of hyperandrogenism; b) participants had no concurrent illness and were not on any prescription or over-the-counter medication that was likely to affect insulin sensitivity or lipids for the preceding 12 weeks; c) participants were advised not to change physical activity or dietary habits during the study period; d) given that all subjects were of Asian ethnicity, overweight was defined as $BMI \geq 24 \text{ kg/m}^2$. e.) all subjects had normal thyroid-stimulating hormone and prolactin levels.
 
exclusion criteria : a) age below 18 years or over 50 years; b) uncontrolled hypertension (blood pressure $\geq 160/100 \text{ mmHg}$); c) signs of liver or renal failure or active liver disease (alanine transaminase (ALT) $> 2.5 \times$ the upper limit of normal values); d) patients who were postmenopausal or pregnant; e) alcohol intake greater than 20 g/day; f) patients who could not complete the intervention or had other conditions that made them ineligible for participation. For example, patients taking glucocorticoid steroids or under treatment for a malignant tumor were excluded.

Subject benefits and possible risks and compensate	
This study is an intervention clinical observation trial. Due to the needs of the treatment of their own diseases, the subjects need to collect venous blood for blood sugar, insulin and other tests. After informed consent, the researchers will collect 1ml of the remaining serum, 1m of plasma and 1ml of urine after testing in the laboratory, so as to avoid repeated blood extraction of the subjects and protect the interests of the subjects to the greatest extent. The drugs used in the study were all conventional treatment drugs for newly diagnosed polycystic ovary syndrome. For the survey subjects, through baseline examination and follow-up, the drug response of patients and the therapeutic effect of improving metabolic and reproductive disorders can be clarified, providing a basis for the postoperative treatment of patients and the selection of drugs for the prevention and treatment of complications. In addition, survey subjects can also pass after 3 months. Follow-up examination to understand the efficacy and safety of its treatment.

Document Date	July 28, 2017

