Statistical analysis

Title of the study	The Effect of GLP-1 Agonists Versus OCs on Reproductive Disorders and Cardiovascular Risks in Overweight PCOS
NTC Number	NCT03151005
Statistical method	Statistical analyses were performed using SPSS 23.0 and GraphPad Prism 8. For normally distributed continuous variables of clinical parameters, variables are described as the mean \pm standard deviation (SD), a paired t-test was used to compare pretreatment and posttreatment values of continuous variables in each of the treatment groups, and between-group differences were compared by an independent sample t-test. For nonnormally distributed continuous variables, the nonparametric Wilcoxon signed-rank test for related samples was used to compare pretreatment and posttreatment values in each of the treatment groups. The chi-square test was used for counting data. To compare the changes in clinical parameters between different treatment groups, the nonparametric Mann-Whitney test was used. Proteomic data analysis was described by proteomic data acquisition and analysis. Protein levels are described as the mean \pm standard error of the mean (SEM), and a paired t-test was used to compare plasma protein levels measured by ELISA. Pvalues <0.05 were considered statistically significant.
Document Date	July 28, 2017

Table 1-Baseline and posttreatment characteristics of clinical parameters after 12-week of treatment.

Characteristics	CPA/EE+Met(n=30)			GLP-1 RA+Met(n=30)		
	Baseline	Posttreatment	Pvalue	Baseline	Posttreatment	Pvalue
Biometric features						
Weight(kg)						
BMI (kg/m ²)						
Waist(cm)						
WHR						
SBP(mm/Hg)						
DBP(mm/Hg)						
Reproductive function						
Dominant follicle,n(%)						
Regular menstruation, n(%)						
Amenorrhoea, n(%)*						
Oligomenorrhoea,n(%)†						
Polycystic ovaries according to Rotterdam criteria, n(%)						
T(nmol/L)						
LH(mIU/ml)						
FSH(mIU/ml)						
LH/FSH						
DHEA-S(ug/dL)						
SHBG (nmol/L)						
FAI						
E2(pg/ml)						
P(ng/ml)						
PRL(ng/ml)						
Biochemical profile of glucose metabolism						
HbA1c(%)						
HbA1c(mmol/mol)						
FBG(mmol/L)						
AUCI						
FINS(uU/ml)						
HOMA-IR						
Biochemical profile of lipid metabolism						
TG(mmol/L)						
TC(mmol/L)						

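### Women can enter with regular cycles or without polycystic ovaries, but SAP Table 1 counts both outcomes over all 30 per arm, so restoration cannot be read off and arm differences are diluted

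*Protocol*

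**What the plan says.** **Eligibility.** Inclusion criterion a) requires a Rotterdam diagnosis "based on the presence of two of three criteria", the three being "oligomenorrhea, clinical or biochemical hyperandrogenism, and polycystic ovaries on ultrasound after exclusion of other endocrine causes of hyperandrogenism". No other criterion requires irregular cycles or abnormal ovaries.

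**Objective.** The second item under Trial objective is "Improve PCOS and establish regular menstrual cycles by reducing weight and correcting metabolic disorders".

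**Tables.** SAP Table 1 has rows beginning "Regular menstruation, n" and "Polycystic ovaries according to Rotterdam criteria, n", each a count with a percentage, at baseline and post-treatment, with a P value within each arm. The column headings put 30 women in each arm ("GLP-1 RA+Met(n=30" in one of them). No row or note limits either outcome to women who were abnormal at baseline. SAP Table 2, which compares changes between arms, has no menstrual row and no ovarian-morphology row.

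**Tests.** For categorical data the SAP says only "The chi-square test was used for counting data". It does not say whether this serves the within-arm or the between-arm comparison, and it names no paired test for counts. The threshold is "Pvalues <0.05 were considered statistically significant".

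**The concern.** Two kinds of eligible woman matter here. One has hyperandrogenism and polycystic ovaries but regular cycles. The other has oligomenorrhoea and hyperandrogenism but normal ovaries. The first cannot have regular cycles established, because she already has them; the second has no polycystic ovaries to resolve. Both stay in the denominator of 30.

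Two things follow. The all-women post-treatment percentage does not estimate what the objective asks about, namely how often regular cycles are established in women who lack them. And if the arms are compared on that percentage, the women already regular add the same amount to both arms on average, which shrinks the visible difference and costs power in a trial of 60.

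**Working it through.** **Inputs from the documents.** Total 60 (protocol, number of cases); 30 per arm (SAP table headings); threshold 0.05 (SAP), taken as two-sided. The one check available on the plan's own figure is 2 × 30 = 60, which agrees. No effect size, event rate or power is given, so the sample size itself cannot be re-derived.

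**Assumed inputs.** f is the share regular at baseline, and these women are taken to stay regular. r is the rate at which the other women become regular. The documents give neither, so ranges are shown.

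**Step 1: what the percentage shows.** Post-treatment share = f + (1 − f)r. Change from baseline = (1 − f)r. With r = 50%:

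| f | Post-treatment share | Change from baseline | True restoration |
|---|---|---|---|
| 0% | 50% | 50 points | 50% |
| 10% | 55% | 45 points | 50% |
| 20% | 60% | 40 points | 50% |
| 30% | 65% | 35 points | 50% |

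The first reading is too high and the second too low. The same algebra applies to polycystic ovaries, with f the share without them at baseline.

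**Step 2: marginal counts do not identify conversions.** Suppose 8/30 are regular at baseline and 20/30 after. If nobody lost regularity, 12 of 22 were restored (55%). If all 8 lost it, 20 of 22 were restored (91%). Table 1 would look the same in both cases. An unpaired chi-square also cannot tell them apart: the pooled share is 28/60 = 0.467, and 0.40² / (0.467 × 0.533 × 2/30) = 9.64 either way. McNemar's statistic is (12 − 0)²/12 = 12.0 in the first case and (20 − 8)²/28 = 5.14 in the second.

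**Step 3: dilution between arms.** Observed difference = (1 − f) × true difference. For a true 30 points:

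- f = 15%: 30 × 0.85 = 25.5 points
- f = 25%: 30 × 0.75 = 22.5 points
- f = 35%: 30 × 0.65 = 19.5 points

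The at-risk denominators, 30 × (1 − f), are 25.5, 22.5 and 19.5 per arm.

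**Step 4: power.** Two-proportion test, pooled variance under the null, two-sided 0.05, with assumed restoration rates of 40% and 75%:

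| f | Difference, all 30 | Power, all 30 | At risk per arm | Power, at risk (35 points) |
|---|---|---|---|---|
| 0% | 35.0 | 79.9% | 30 | 79.9% |
| 10% | 31.5 | 72.0% | 27 | 75.4% |
| 20% | 28.0 | 63.5% | 24 | 70.1% |
| 30% | 24.5 | 54.8% | 21 | 64.0% |
| 40% | 21.0 | 46.1% | 18 | 57.0% |

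With 50% against 80%, power at f = 20% is 54.6% over all 30 and 59.1% at risk. Restriction recovers the full difference but only part of the lost power.

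**Step 5: false positives.** In 200,000 simulated trials per setting, with 50% restoration in both arms and f from 0% to 40%, the all-women chi-square test rejected in 4.9% to 5.1% of trials. The restricted test rejected in 5.1% to 5.3%.

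**The case against.** The strongest reply is that Table 1 prints baseline beside post-treatment. If no woman loses regularity, restoration can be recovered as (post − baseline)/(30 − baseline), so only a reader who ignores the adjacent column is misled. That holds only under the stated condition. Women regular at baseline can worsen, and step 2 shows how far the answer then moves.

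A second reply is that the SAP sets out no between-arm menstrual comparison: Table 2 has no such row, and the chi-square sentence names no comparison. This stands, and it is why the dilution is stated conditionally. It also means that an outcome named in the objective has no planned contrast between arms, which leaves the reader with two percentages side by side.

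Third, an all-women summary is a legitimate description, and a baseline-stratified analysis of all 60 is a valid alternative. Both points stand. In a Mantel–Haenszel analysis stratified by baseline status, a stratum in which everyone stays regular contributes nothing, so the result matches the restricted one in that case.

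Three stronger readings are tempting and are not supported:

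- *Women already regular are counted as treatment successes.* The SAP defines no responder or success endpoint.
- *Chance imbalance in baseline regularity confounds the comparison.* Allocation is random, so such imbalance is ordinary sampling error already carried by the standard error; step 5 shows no inflation.
- *The baseline row proves that the plan expects regular women.* Every row of Table 1 has a baseline column, and this one could read zero.

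**Conclusion.** The point holds as a question of estimand and reporting, with a conservative effect on any comparison between arms. The entry rule admits women in whom regular cycles cannot be established or polycystic ovaries cannot be resolved, and the planned rows neither separate them out nor allow them to be separated afterwards from the printed counts.

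A true 30-point difference in restoration would appear as 22.5 points if 25% are regular at baseline and stay so, and as 25.5 to 19.5 points for shares of 15% to 35%. At a 20% share, with restoration rates of 40% and 75%, analysing women irregular at baseline raises power from 63.5% to 70.1%. The direction follows from the entry rule and the table layout; the sizes rest on assumed shares and rates. If nearly all enrolled women prove to be irregular at baseline, the effect on the menstrual row is small.

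Separately, an unpaired chi-square test does not suit before/after counts in the same women. How cyclic CPA/EE itself affects bleeding is a different question and is not part of this point.

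**What to change.** In the SAP:

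1. Add a row for *restored regular menstruation*: regular at 3 months among women amenorrhoeic or oligomenorrhoeic at baseline.
2. Add a row for *resolution of polycystic ovaries*: absent at 3 months among women who had them at baseline.
3. Print the denominator for each row and arm, and compare both outcomes between arms. The subsets are fixed by baseline status, so the comparison remains randomised.
4. Keep the all-women rows as description, and state how many women regular at baseline lost regularity.
5. Use McNemar's test in place of chi-square for within-arm before/after counts.

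Entry criteria, treatment and visits need not change. The Study design section already has ultrasound at baseline and 3 months, and Table 1 already presupposes menstrual status at both times. That section lists menstrual history by name only at the 1-month visit, so its recording at baseline and 3 months should be confirmed.

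The cost is SAP wording and two table rows. The downside is a smaller denominator, about 20 to 26 per arm for baseline shares of 35% to 15%. Under the assumed rates this is more than offset by removing the dilution, but the estimates remain imprecise at this trial size.

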Statistical analysis

Title of the study	The Effect of GLP-1 Agonists Versus OCs on Reproductive Disorders and Cardiovascular Risks in Overweight PCOS
NTC Number	NCT03151005
Statistical method	Statistical analyses were performed using SPSS 23.0 and GraphPad Prism 8. For normally distributed continuous variables of clinical parameters, variables are described as the mean \pm standard deviation (SD), a paired t-test was used to compare pretreatment and posttreatment values of continuous variables in each of the treatment groups, and between-group differences were compared by an independent sample t-test. For nonnormally distributed continuous variables, the nonparametric Wilcoxon signed-rank test for related samples was used to compare pretreatment and posttreatment values in each of the treatment groups. The chi-square test was used for counting data. To compare the changes in clinical parameters between different treatment groups, the nonparametric Mann-Whitney test was used. Proteomic data analysis was described by proteomic data acquisition and analysis. Protein levels are described as the mean \pm standard error of the mean (SEM), and a paired t-test was used to compare plasma protein levels measured by ELISA. Pvalues <0.05 were considered statistically significant.
Document Date	July 28, 2017

Table 1-Baseline and posttreatment characteristics of clinical parameters after 12-week of treatment.

Characteristics	CPA/EE+Met(n=30)			GLP-1 RA+Met(n=30)		
	Baseline	Posttreatment	Pvalue	Baseline	Posttreatment	Pvalue
Biometric features						
Weight(kg)						
BMI (kg/m ²)						
Waist(cm)						
WHR						
SBP(mm/Hg)						
DBP(mm/Hg)						
Reproductive function						
Dominant follicle,n(%)						
Regular menstruation, n(%)						
Amenorrhoea, n(%)*						
Oligomenorrhoea,n(%)†						
Polycystic ovaries according to Rotterdam criteria, n(%)						
T(nmol/L)						
LH(mIU/ml)						
FSH(mIU/ml)						
LH/FSH						
DHEA-S(ug/dL)						
SHBG (nmol/L)						
FAI						
E2(pg/ml)						
P(ng/ml)						
PRL(ng/ml)						
Biochemical profile of glucose metabolism						
HbA1c(%)						
HbA1c(mmol/mol)						
FBG(mmol/L)						
AUCI						
FINS(uU/ml)						
HOMA-IR						
Biochemical profile of lipid metabolism						
TG(mmol/L)						
TC(mmol/L)						

Data are mean \pm SD or n(%). BMI, body mass index; WHR, waist-to-hip ratio; SBP, systolic blood pressure; DBP, diastolic blood pressure; T, testosterone; LH, luteinizing hormone; FSH, follicle-stimulating hormone; DHEA-S, dehydroepiandrosterone; SHBG, sex hormone-binding globulin; FAI, free androgen index; E2, estradiol; P, progesterone; PRL, prolactin. HbA1c, hemoglobin A1c; FBG, fasting blood glucose; FINS, fasting insulin; AUCI, area under curve of insulin; HOMA-IR, homoeostasis model assessment of insulin resistance; TG, triglycerides; TC, total cholesterol

Table 2-Characteristics change after treatment in this study.

Characteristics	CPA/EE +Met (n=30)	GLP-1 RA +Met (n=30)	t/z	Pvalue
Biometric features				
△Weight (kg)				
△BMI (kg/m ²)				
△Waist (cm)				
△WHR				
△SBP (mm/Hg)				
△DBP (mm/Hg)				
Sex hormones and related indicators				
△T (nmol/L)				
△LH (mIU/ml)				
AFSH (mIU/ml)				
ALH/FSH				
△DHEA-S (ug/dL)				
△SHBG (nmol/L)				
△FAI				
△E2 (pg/ml)				
△P (ng/ml)				
△PRL (ng/ml)				
Biochemical profile of lipid metabolism				
△TG (mmol/L)				
△TC (mmol/L)

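### The SAP names no paired test for Table 1's before-versus-after counts; its only count rule is an unqualified chi-square test

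*SAP*

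**What the plan says.** The Statistical method section of the SAP has one sentence on counts: "The chi-square test was used for counting data". It does not say whether the comparison is within or between arms, whether the data are paired, or what to do when counts are small.

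For continuous data the same section does state the pairing. For normally distributed variables, "a paired t-test was used to compare pretreatment and posttreatment values of continuous variables in each of the treatment groups". For the others, "the nonparametric Wilcoxon signed-rank test for related samples was used". The significance rule is "Pvalues <0.05 were considered statistically significant".

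The shell headed "Table 1-Baseline and posttreatment characteristics of clinical parameters after 12-week of treatment" has baseline, posttreatment and P value columns inside each arm, under a single n=30. Five of its rows are counts with percentages: dominant follicle, regular menstruation ("Regular menstruation, n"), amenorrhoea, oligomenorrhoea and polycystic ovaries ("Polycystic ovaries according to Rotterdam criteria, n"). The between-arm shell, "Table 2-Characteristics change after treatment in this study", shows no count rows.

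**The concern.** Each of the five count rows measures the same 30 women twice, so the two proportions in a row are correlated. The ordinary chi-square test assumes two independent groups. It uses only the two totals, so it returns the same P value whether seven women gained a feature and none lost it, or many gained it and nearly as many lost it. A paired test works from exactly that split.

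Five rows in two arms make ten P values. In the shells as shown they are the only P values on counts. A regular menstrual cycle is part of the Trial objective in the protocol, so these rows are not incidental. With the usual positive within-woman correlation the unpaired test is conservative, and the main risk is a real within-arm change reported as not significant. With zero or negative correlation, or with small counts, P can instead be too small. As written, two analysts could follow the SAP and report different P values from the same data.

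**Working it through.** **Inputs from the documents.** 30 women per arm, the same at both visits (Table 1); cut-off 0.05 (Statistical method), taken as two-sided because the SAP does not say. The documents give no event rates, correlations, effect size or power, so there is no planned figure to reproduce. All counts, rates and correlations below are assumptions.

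**Formulas.** Let b be the number of women who gain the feature and c the number who lose it.
- Ordinary (uncorrected Pearson) chi-square: z = (p2 − p1) / √[p(1 − p) × 2/30], with p the pooled proportion. Pairing does not enter.
- McNemar, asymptotic: (b − c)² / (b + c) on 1 degree of freedom.
- McNemar, exact: two-sided binomial P for b out of b + c at one half.
- McNemar, mid-P: exact P minus the binomial probability of the observed split.

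**One table in full: 6/30 to 13/30, b = 8, c = 1** (5 women with the feature at both visits, 16 at neither).
- Within-woman correlation: phi = (5×16 − 8×1) / √(13×17×6×24) = 72/178.4 = 0.40.
- Chi-square: p = 19/60 = 0.317; z = 0.2333 / √(0.317 × 0.683 × 2/30) = 1.94; P = 0.052.
- McNemar, asymptotic: 7²/9 = 5.44; P = 0.020.
- McNemar, exact: 2 × (1 + 9)/512 = 0.0391.
- McNemar, mid-P: 0.0391 − 9/512 = 0.0391 − 0.0176 = 0.0215.
- 95% Newcombe score interval for the 23.3-point rise: −0.2 to 43.7 points unpaired, 5.1 to 39.7 paired.

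**Other single tables**

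| Change | Gained : lost | phi | Chi-square | Mid-P | Exact |
|---|---|---|---|---|---|
| 6 to 12 | 7 : 1 | 0.44 | 0.091 | 0.039 | 0.070 |
| 0 to 4 | 4 : 0 | not defined | 0.038 | 0.0625 | 0.125 |
| 1 to 6 | 6 : 1 | −0.09 | 0.044 | 0.070 | 0.125 |
| 10 to 18 | 12 : 4 | 0 | 0.038 | 0.049 | 0.077 |

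**Rejection rate when nothing changes** (nominal 5%; exact enumeration of all tables of 30 pairs)

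| phi | Chi-square | Mid-P |
|---|---|---|
| 0.5 | 0.6–0.8% (rates 10–50%) | 2.4–3.7% (rates 20–50%) |
| 0.3 | 1.9–2.2% (rates 10–50%) | 3.5–4.2% (rates 20–50%) |
| 0 | 4.9–5.4% (rates 10–50%) | 4.1–4.7% (rates 20–50%) |
| −0.2 | 7.1–7.6% (rates 20–50%) | 4.3–4.7% (rates 20–50%) |

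At a 10% rate mid-P rejects 0.6% (phi 0.5), 1.5% (phi 0.3) and 2.8% (phi 0).

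**Power**

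| True change | phi | Chi-square | Mid-P | Exact |
|---|---|---|---|---|
| 20% to 45% | 0.45 | 56% | 80% | 69% |
| 20% to 45% | 0.30 | 55% | 67% | 57% |
| 20% to 45% | 0.15 | 55% | 58% | 49% |
| 20% to 45% | 0 | 55% | 52% | 43% |
| 10% to 30% | 0.44 | 49% | 69% | 53% |
| 12% to 60% | 0.18 | over 99% | over 99% | over 99% |

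**The case against.** The strongest reply is that this is silence, not a demonstrated error. McNemar's test is itself a chi-square test and may have been meant. The argument that the SAP states pairing wherever it intends it is weakened because the same section also labels the independent-samples t-test explicitly, so wording alone does not settle the intent. That stands. It changes the remedy only slightly: if McNemar was meant, the sentence should say so. If the rule was meant only for between-arm counts, Table 1's ten count P values have no test at all.

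Second, two of the examples in which chi-square is too small (0 to 4 and 1 to 6) are mainly small-count problems. Their smallest expected counts are 2 and 3.5, and an unpaired Fisher test already gives 0.112 and 0.103. In the 10 to 18 example chi-square and mid-P both fall below 0.05. The 7.1–7.6% rejection rate needs negative correlation and the uncorrected statistic; with continuity correction it is 3.7–4.4%. This stands too, so the case rests mainly on lost power and not on false positives.

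Third, part of the gain comes from choosing mid-P. Exact McNemar clearly beats chi-square only at the highest assumed correlation for 20% to 45%, and does worse at 0.15 and below. This is a fair reason to report exact power alongside, but not a reason to analyse paired data as unpaired.

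Finally, the shells may be incomplete, and within-arm P values do not compare the treatments. Both are true, and both limit how serious the point is.

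**Conclusion.** The point holds. The SAP's only count rule does not specify a paired test for the five count rows where Table 1 needs one, and read in its ordinary form it gives a test whose assumption of independent groups is not met. The result can cross the 0.05 line: 0.052 against 0.021 (mid-P) or 0.039 (exact) for the same assumed data. At within-woman correlations of 0.30 to 0.45, chi-square loses about 12 to 24 points of power against mid-P for a rise from 20% to 45% (55% v 67%; 56% v 80%). Near zero correlation the difference disappears or slightly reverses, and for a change as large as 12% to 60% it does not matter.

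These sizes depend on assumed rates and pairings, and on the uncorrected chi-square. What is certain is that the plan does not name a paired test. It should be fixed, but no conclusion about one arm against the other depends on it.

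**What to change.** Replace the count sentence in the Statistical method section with wording such as: *Within-arm baseline-versus-posttreatment counts are compared by the mid-P McNemar test, reporting the numbers who gained and lost the feature, with a paired 95% confidence interval for the difference in proportions (Newcombe paired score interval). The chi-square test, or Fisher's exact test when any expected count is below 5, is used only for between-arm counts.* If McNemar's test was already intended, naming it is the essential part.

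The cost is one sentence. It needs no extra patients or data, because the gained and lost counts are already in each woman's records. There are three small downsides:
- slightly less power than chi-square when within-woman correlation is near zero (52% v 55% for 20% to 45%);
- conservatism of mid-P for rare features (0.6–1.5% rejection at a 10% rate with phi of 0.5 to 0.3);
- a short hand calculation, as shown for the 8:1 split, if the software does not report mid-P.

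The change corrects the within-arm P values only. It does not make them evidence of a difference between the randomised arms.

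### Changes are compared between arms without adjusting for the baseline already collected, and no between-arm difference with a confidence interval is planned

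*SAP*

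**What the plan says.** The Protocol (Study design) states that eligible patients "were randomly assigned to GLP-1RA + metformin or Diane-35 + metformin", after body measurements, blood pressure and blood tests had been taken. The Table 1 shell in the SAP has a baseline column for every variable that Table 2 later shows as a change.

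The SAP (Statistical method) describes these tests for continuous clinical variables:

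- Within arms, for normal variables: "a paired t-test was used to compare pretreatment and posttreatment values of continuous variables in each of the treatment groups".
- Between arms, in the same sentence: "between-group differences were compared by an independent sample t-test".
- Within arms, otherwise: "For nonnormally distributed continuous variables, the nonparametric Wilcoxon signed-rank test for related samples was used".
- For changes between arms, without any condition on distribution: "To compare the changes in clinical parameters between different treatment groups, the nonparametric Mann-Whitney test was used".

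The only decision criterion is "Pvalues <0.05 were considered statistically significant". The Table 2 shell ("Characteristics change after treatment in this study") has one column per arm (n=30 each), a t/z column and a P value column. No covariate-adjusted model and no confidence interval appears in either document.

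**The concern.** Three things are missing or unsettled.

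1. **Baseline adjustment.** Subtracting the baseline is not the same as adjusting for it. A change score fixes the baseline slope at 1. Where the true slope is lower, the contrast carries avoidable noise and keeps part of any chance baseline imbalance. With 30 per arm, precision is scarce.

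2. **An estimate.** A test statistic and a P value do not show how large the between-arm effect is, or which effects a non-significant row leaves open. With no sample-size derivation for the 60 cases, ambiguous null rows are likely.

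3. **The test for each row.** The t/z heading implies a t-test for some rows, and the text ties t-tests to normal variables, but the sentence on changes assigns Mann-Whitney to all of them. No normality criterion is given, so the choice could be made after seeing the data.

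**Working it through.** **Inputs.** From the documents: 30 per arm, two unadjusted between-arm tests, significance at 0.05 (taken as two-sided). The plan gives no SD, correlation, effect size or power, so there is no figure of its own to reproduce. The correlation r between baseline and 12-week value, the SDs and the distributions below are assumptions, with r = 0.3, 0.5, 0.7 and 0.9 throughout.

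**Variance.** In baseline-SD units, let k = SD(post)/SD(baseline). Then

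- Var(change) = 1 + k² − 2kr
- Var(ANCOVA residual) = k²(1 − r²), with slope rk

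At k = 1 the ratio is (1 − r²)/(2 − 2r) = (1 + r)/2, giving 0.65, 0.75, 0.85, 0.95. At k = 0.8 it is 0.50, 0.57, 0.63, 0.61; at k = 1.2 it is 0.76, 0.87, 0.97, 0.98. With posttreatment SDs of 1.5 in one arm and 0.7 in the other, the simulated ratio is 0.75, 0.85, 0.95, 1.02.

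**Interval half-width (k = 1).** t(0.975) × residual SD × √(2/30), with 58 df for change and 57 for ANCOVA. At r = 0.5 the residual SDs are √(2 × 0.5) = 1.000 and √(1 − 0.25) = 0.866.

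| r | Change score (SD) | ANCOVA (SD) |
|---|---|---|
| 0.3 | 0.612 | 0.493 |
| 0.5 | 0.517 | 0.448 |
| 0.7 | 0.400 | 0.369 |
| 0.9 | 0.231 | 0.225 |

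**Chance imbalance.** One standard error of baseline difference is √(2/30) = 0.26 SD. It shifts the change-score contrast by (1 − r) times that: 0.18, 0.13, 0.08, 0.03 SD.

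**Power.** Simulation, 20,000 trials per setting, 30 per arm; effect 0.6 SD, or 0.32 SD at r = 0.9. Log-normal effects are on the log scale.

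| Data | Method | r = 0.3 | 0.5 | 0.7 | 0.9 |
|---|---|---|---|---|---|
| Normal | Mann-Whitney on change | 46% | 60% | 81% | 75% |
| Normal | ANCOVA | 66% | 75% | 88% | 79% |
| Log-normal, log SD 0.6 | Mann-Whitney on raw change | 49% | 61% | 82% | 73% |
| Log-normal, log SD 0.6 | ANCOVA, log scale | 66% | 74% | 89% | 78% |
| Log-normal, log SD 0.6 | ANCOVA, raw scale | 58% | 65% | 80% | 66% |
| t, 3 df | Mann-Whitney on change | 67% | 81% | 96% | 94% |
| t, 3 df | ANCOVA | 73% | 80% | 90% | 83% |

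With a slope of exactly 1 (r = 0.7, k = 1/0.7, 0.6 SD effect) there is no gain over the t-test: Mann-Whitney 58%, t-test on change 61%, ANCOVA 60%.

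**Validity.** Type I error, with equal posttreatment SDs and with SDs of 1.5 and 0.7, normal and t(3) data: ANCOVA 4.4% to 5.2%, Mann-Whitney 4.5% to 5.3%. A t-test on rank residuals reaches 5.9% to 10.6% (normal) and 5.4% to 9.0% (t, 3 df) when the SDs differ.

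**Interval for the planned test.** The Hodges-Lehmann 95% interval (317th and 584th of the 30 × 30 = 900 ordered pairwise differences) covers 94.7% to 95.5%. Median half-widths are 0.63, 0.53, 0.41, 0.24 SD for normal data, against 0.50, 0.45, 0.37, 0.23 for ANCOVA. For t(3) data they are 0.49, 0.41, 0.31, 0.18 against 0.44, 0.40, 0.33, 0.20.

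**The case against.** The planned tests are valid, and with no correlations or distributions in the documents the size of any gain is assumed. A rank test as the main analysis is defensible where the shape is unknown. Three points narrow the claim:

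- **Comparator.** Part of the power gap for normal data comes from comparing ANCOVA with Mann-Whitney. If t/z means a t-test for normal changes, the fair comparison is a t-test on change. A separate simulation gives 50/63/83/79% for that test against 67/74/88/80% for ANCOVA. The gain at low r remains; at r = 0.9 it is about 1 point.
- **Heavy tails and unlogged skew.** For t(3) data, Mann-Whitney is already level or slightly ahead at r = 0.5 (80.7% against 79.5%). For log-normal data left unlogged, ANCOVA falls behind at r = 0.7 (79.8% against 81.7%), and by more at log SD 1.0 (46/53/64/51% against 47/60/79/69%). The proposal therefore depends on choosing the right variables to log, and the documents describe no distributions.
- **Recoverable interval.** If Table 2 reports mean ± SD, as the note under Table 1 does, a reader can compute an unadjusted interval. It would not correspond to a Mann-Whitney P value.

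These limit how much ANCOVA gains and for which variables. They do not supply an effect estimate or settle the test. The SAP's sentence on changes is unconditional, so Mann-Whitney is a fair comparator for the plan as written. Rows of Table 2 may have been lost in text extraction, but the point rests on its column headings, which are intact.

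**Conclusion.** The concern holds. The plan does not adjust for a baseline it collects, plans no between-arm difference with an interval, and leaves the test per row undecided. This is a loss of precision and interpretability; type I error is not at risk.

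Under equal SDs the variance saving is 35%, 25%, 15% and 5% at r = 0.3, 0.5, 0.7 and 0.9: material at low to moderate correlation, small for variables that track strongly. Weight, BMI and waist may be of that kind, but this is an assumption. The gain disappears when the slope is near 1 and reverses for heavy-tailed, strongly tracking variables. The need for an estimate with an interval does not depend on r. Confidence in the size of the gain is medium because the correlations are unknown.

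**What to change.** 1. For each continuous variable compared between arms (the Table 2 rows, and the Table 1 glucose variables if they are compared too), make the main analysis an ANCOVA of the 12-week value on treatment and that variable's own baseline.
2. Name in advance the right-skewed variables to be log-transformed. TG, SHBG and FAI are candidates; the other hormones and the insulin measures need the same decision.
3. Add to Table 2 the adjusted difference (or ratio) with its 95% CI beside the P value.
4. Keep Mann-Whitney on changes as a prespecified sensitivity analysis, with a Hodges-Lehmann shift and 95% CI. This covers the heavy-tailed and skewed cases.
5. State the normality criterion and the test behind each t/z entry.
6. Do not use a t-test on rank residuals as the fallback: it gives no effect on the measurement scale, and its type I error rises when the arms' SDs differ.

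The count outcomes have the same gap ("The chi-square test was used for counting data" is all that is said), and a risk difference with a CI would close it.

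**Cost.** SAP wording and a routine model in SPSS, which the SAP already names; no extra data. Each model uses one degree of freedom and needs a residual check. The price is little or no gain where the slope is near 1 (ratio 1.02 at r = 0.9 with unequal arm SDs). Power is lower than Mann-Whitney for heavy-tailed variables that track strongly (90% against 96% at r = 0.7; 83% against 94% at r = 0.9) and for strongly skewed variables left unlogged (66% against 73% at r = 0.9, log SD 0.6).
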